Unique study approval ID (Sweden): 2019-05490

Official title: Improving care for children with congenital heart disease by cardiovascular biomarker profiling and advanced non-invasive cardiac imaging techniques.

Statistical analysis plan (date): 25th of Oct. 2020

Study protocol summary:

Study type & outcome measure for cases:

- Case-control study to evaluate diagnostic usefulness of non-invasive cardiac imaging measures and cardiovascular biomarkers in children.
- Need for open heart surgery or cardiac catheter intervention to treat predefined congenital heart disease lesions leading to pulmonary over-circulation (as below).

Enrolment:

After local advertisement and written informed consent (dedicated healthcare regions in Sweden).

Controls (0-17 years) without history or presence of cardiovascular disease at enrolment:

Number of assessments: 1 (at enrolment)

Type of assessments in local paediatric cardiology ambulatory / out-patient clinic settings:

1. Clinical evaluation cardiovascular examination by paediatric cardiologist
2. Standard 12 lead ECG recording
3. Transthoracic echocardiography examination (predefined standard paediatric protocol including but not limited to 2D, Doppler, TDI)
4. Cardiac magnetic resonance (CMR) evaluation of the heart using predefined sequence protocol (including 4D flow assessments) for comparison to cases reaching outcomes (matched subgroup)
5. Peripheral blood sampling for cardiovascular biomarker batch analysis (O-link proximity extension assay of 96 markers and quantitative analysis of selected biomarkers, e.g. NT-pro-BNP)
6. Optional saliva sampling at enrolment and/or retrieval of dried blood samples from neonatal screening laboratory if available for batch analysis and comparison to standard blood sample cardiovascular biomarkers (O-link proximity extension assay of 96 markers and quantitative analysis of selected biomarkers, e.g. NT-pro-BNP)

Cases (0-17 years) without treated congenital heart disease by open heart surgery or cardiac catheter intervention at enrolment:

Included lesions of congenital heart disease leading to pulmonary over-circulation:

- Atrial septal defect (ASD)
- Ventricular septal defect (VSD)
- Patent ductus arteriosus (PDA)
- Partial anomalous pulmonary venous drainage (PAPVD)
- Aorto-pulmonary window (APW)

Number of assessments:

- Minimum 2 (at enrolment and 6-12 months after outcome is reached)
- Maximum 4 (at enrolment and annually to a max. follow-up of 3 years if not reaching outcome)

Type of assessments in local paediatric cardiology hospital / out-patient clinic settings:

1. Clinical evaluation cardiovascular examination by paediatric cardiologist
2. Standard 12 lead ECG recording
3. Transthoracic echocardiography examination (predefined standard paediatric protocol including but not limited to 2D, Doppler, TDI)
4. Cardiac magnetic resonance (CMR) evaluation of the heart using predefined sequence protocol (including 4D flow assessments) for subjects reaching outcome (undergoing open heart surgery / cardiac catheter intervention) on hospital admission before treatment and 6-12 months after intervention in ambulatory setting.
5. Peripheral blood sampling for later cardiovascular biomarker batch analysis (proximity extension assay and quantitative analysis for selected biomarkers, e.g. NT-pro-BNP)
6. Optional saliva sampling at enrolment and/or retrieval of dried blood samples from neonatal screening laboratory if available as well as optional cardiovascular tissue sampling at time of open heart surgery for batch analysis and comparison to standard blood sample cardiovascular biomarkers (O-link proximity extension assay of 96 markers and quantitative analysis of selected biomarkers, e.g. NT-pro-BNP)

Table summarizing study protocol:

Type of assessment	Subjects	Enrolment	1 year	2 years	3 years
Clinical evaluation	Controls	X	-	-	-
	Cases	X	X	X	X
12-lead ECG	Controls	X	-	-	-
	Cases	X	X	X	X
Transthoracic echocardiography	Controls	X	-	-	-
	Cases	X	X	X	X
Cardiac magnetic resonance *	Controls	X = 1 assessment for controls at enrolment			
	Cases	X = 2 assessments for cases reaching outcome (1 st on admission for intervention & 2 nd 6-12 months post intervention)			
Peripheral blood sampling	Controls	X	-	-	-
	Cases	X	X	X	X

Optional saliva / dried blood sampling	Controls	X	-	-	-
	Cases	X	X	X	X
Optional cardiovascular tissue sampling	Controls	-			
	Cases	X (1 sample for subgroup of cases undergoing open heart surgery)			

*) Subgroup of cases reaching outcome during study and subgroup of matched controls.

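### Comparing archived neonatal dried blood with blood first drawn at enrolment mixes sample type with age at draw and storage time, and for cases the text and table disagree on when optional samples are taken

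*Protocol*

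**What the plan says.** For controls, item 6 of the Protocol's list of assessments offers optional saliva at enrolment and "retrieval of dried blood samples from neonatal screening laboratory if available for batch analysis and comparison to standard blood sample cardiovascular biomarkers". For cases, item 6 has the same elements and adds tissue: "Optional saliva sampling at enrolment and/or retrieval of dried blood samples from neonatal screening laboratory if available as well as optional cardiovascular tissue sampling", again for comparison with standard blood. The text names no source of dried blood other than the neonatal screening laboratory.

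Entry ages are wide in both groups: "Controls (0-17 years) without history or presence of cardiovascular disease at enrolment" and "Cases (0-17 years) without treated congenital heart disease by open heart surgery or cardiac catheter intervention at enrolment". Controls have standard blood once: "Number of assessments: 1 (at enrolment". Cases have it at enrolment and, in the table, at 1, 2 and 3 years, in line with "Maximum 4 (at enrolment and annually to a max. follow-up of 3 years if not reaching outcome".

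The summary table has one combined row, "Optional saliva / dried blood sampling". Controls are marked at enrolment only; cases are marked at enrolment and at 1, 2 and 3 years.

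The SAP lists group tests, changes over follow-up in cases, logistic regression and ROC/AUC analysis. It has no analysis between sample types and no term for age at draw or storage time. Its one line on storage asks for standardised conditions until the batch assay and does not mention samples already archived elsewhere.

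**The concern.** A comparison of two sample types is informative about sample type when both are taken from the child at about the same time. Here one is a newborn sample held in an archive and the other is drawn when the child joins the study, possibly many years later. If the two disagree, the cause could be the dried matrix, the child's growth, years of storage or, in a case, the course of the lesion. A reader could take the disagreement as evidence against dried blood when ageing or storage alone might have produced it.

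The text and table conflict is a separate, practical matter. A site following the text collects one saliva sample per case. A site following the table could collect up to four optional samples per case, without being told whether these are saliva, new dried spots or both.

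**Working it through.** The documents give no sample size, event count or agreement figure on this point, so there is no plan figure to reproduce. Three checks were made.

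**1. The gap between samples.**
- Neonatal sample: age about 0. Enrolment sample: age 0 to 17 years (Protocol, Controls and Cases headings).
- Gap at enrolment: 0 - 0 = 0 to 17 - 0 = 17 years, or just under 18 if age 17 means completed years.
- The documents do not say which standard sample is the comparator for cases. If it were the 3-year sample, the largest gap would be 17 + 3 = 20 years, or just under 18 + 3 = 21.

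**2. What a within-child difference can estimate.** Assume both samples from a child are assayed in one batch and that effects are linear on the analysis scale. Let a be age at enrolment and c the time from enrolment to assay.

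| Term | Dried neonatal | Standard at enrolment | Difference |
|---|---|---|---|
| Sample type (effect τ) | 1 | 0 | 1 |
| Age at draw (effect β) | 0 | a | -a |
| Storage time (effect γ) | a + c | c | a |

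Expected difference = τ - βa + γa = τ + (γ - β)a.

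- There are three effects but only two estimable quantities: the intercept τ and the slope (γ - β). Age and storage effects cannot be separated within child.
- The crude mean difference is τ + (γ - β) × mean age at enrolment. It equals τ only if mean age is near zero or the two effects happen to cancel.
- τ itself is the value at a = 0, so it depends on children enrolled near birth or on extrapolating to them.
- A numerical check with 200 simulated children aged 0 to 18 gave rank 2 for 3 terms and a correlation of 1.0 between age gap and extra storage time. This held both with c fixed at 1.5 years and with c varying from 0 to 3 years.
- In cases, disease course also changes over a and adds to the slope. Controls have no cardiovascular disease, so this does not apply to them.

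**3. Text against table.**

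| Group | Text, item 6 | Table row |
|---|---|---|
| Controls | Saliva at enrolment; archived newborn dried blood | Enrolment |
| Cases | Saliva at enrolment; archived newborn dried blood | Enrolment, 1, 2 and 3 years |

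For controls the two agree on saliva. For cases the table has 4 marks against 1 saliva time point in the text, which leaves 4 - 1 = 3 marks unexplained. Retrieving one archived newborn sample cannot supply annual marks.

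**The case against.** The strongest reply is that the documents do not specify the analysis being criticised. Item 6 says only that samples will be compared. A reader might infer that the study means to show dried blood can replace peripheral blood. Neither document states that aim, and the SAP lists no agreement or correlation analysis between sample types. The stated aim is early prediction, which a newborn sample could serve well, and the comparison might mean predictive value or case-control contrast. This stands as a limit on the point: what is planned is an undefined comparison, not a declared replacement study. It does not remove the problem, because the most direct reading of the stated comparison is within child, and nothing restricts or adjusts it.

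A reader might also infer that sample type can never be separated from age. That is too strong. Entry starts at age 0 in both groups, and the algebra above shows that children enrolled near birth identify the sample-type effect. Standard samples from different children could also inform the age effect on means. No such modelling is planned.

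It is tempting to put a figure on the loss of correlation. Suppose a same-visit correlation of 0.90, and sample-type error independent of change over time. A within-child correlation of 0.2 then gives 0.90 × 0.2 = 0.18, one of 0.8 gives 0.90 × 0.8 = 0.72, and a zero gap gives 0.90 × 1 = 0.90. All these inputs are assumed. The documents give none of them, nor an age distribution, so the range illustrates direction only.

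Finally, one might read the table as promising fresh dried spots, and so same-visit dried-blood pairs, at each annual visit. The row is a merged optional heading and its later marks may mean saliva only. The text describes neither, so such pairs cannot be presumed. On any reading the row needs correction or explanation.

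**Conclusion.** The point holds in limited form. Except in children enrolled as newborns, a direct within-child comparison of neonatal dried blood with standard blood mixes sample type with age at draw and storage time and, in cases, disease course. A weak correlation or a mean shift could not then be attributed to sample type. That age and storage are inseparable within child rests on the one-batch and linearity assumptions. The gap itself follows from the entry ages.

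The gap is about 0 to 17 years at enrolment, but the resulting bias cannot be sized, and how many children sit at the long end is unknown. The text and table conflict is real, is confined to cases, and changes what sites would collect.

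The samples are optional and the comparison is secondary. The main case-control and prediction analyses are not affected. The change is worth making because a stated comparison could mislead and two parts of the Protocol disagree.

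**What to change.** 1. In the SAP, define the comparison in item 6. Limit any direct comparison of saliva or dried blood with standard blood to samples taken at the same visit. That means saliva against blood at enrolment, plus later same-visit pairs if the table's schedule is confirmed. State that the tissue comparison for cases is unaffected by this limit.
2. Use neonatal dried blood for direct comparison only in children enrolled as newborns. Otherwise analyse it in two ways: as an early predictor of outcome in cases, and as a case-control comparison within neonatal samples. Age at draw is alike in the latter. Storage time should be a covariate there, because birth years may differ between groups and matching is described only for the CMR subgroup.
3. Reconcile the cases row of the table with item 6, stating which sample type is collected at which visit.

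The cost is SAP wording and one table row. The downside is that few or no direct dried-blood pairs may remain, depending on how many children are enrolled as newborns.

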Unique study approval ID (Sweden): 2019-05490

Official title: Improving care for children with congenital heart disease by cardiovascular biomarker profiling and advanced non-invasive cardiac imaging techniques.

Statistical analysis plan (date): 25th of Oct. 2020

Aims:

Diagnostic test evaluations of the cardiovascular system in paediatric controls and cases of defined congenital heart disease lesions, in line with e.g. STARD guidelines, to improve the early prediction of the studied outcome (need for open heart surgery or cardiac catheter intervention in cases).

Diagnostic methods:

1. Echocardiography evaluation:

- selected echocardiographic measure (test individual measures) will be selected to predict outcome (need for open heart surgery or cardiac catheter intervention)

- selected echocardiographic measures (test group of measures) will be selected to predict outcome (as above)

2. Cardiac magnetic resonance (CMR) evaluation:

- selected CMR measure (test individual measures) will be selected to predict outcome (as above)

- selected CMR measures (test group of measures) will be selected to predict outcome (as above)

3. Cardiovascular biomarkers:

- selected cardiovascular biomarker (test individual markers) will be selected to predict outcome (as above)

- selected cardiovascular biomarkers (test groups of markers) will be selected to predict outcome (as above)

Data collection:

- estimation of sample size based on previous studies (power 0.8, alpha 0.05)

- clinical data collection according to predefined criteria (anonymised electronic database)

- electronic storage of echocardiography / cardiac magnetic resonance imaging for analysis

- storage of cardiovascular biomarker samples under standardised conditions until batch analysis

- anonymised data analysis using established statistical methods

Data analysis:

- descriptive statistics / frequency tables of all enrolled subjects (n, %, mean/SD, median/IQR).

- parametric / non-parametric tests to compare controls and cases and changes in cases over follow-up period of study

- logistic regression modelling to identify risk factors / create models that are suitable to predict outcome in cases (need for open heart surgery or cardiac catheter intervention)

- receiver operating characteristics curves (ROC) / area under the curve (AUC) analysis for proposed new diagnostic tests that may help to predict outcome in cases (see above)
- propose risk factor scoring system to predict outcome in cases (see above)

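### The plan does not stop children whose procedure is already decided at enrolment from counting as predicted events, so AUCs and the risk score could be biased upward by an unknown amount

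*SAP*

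**What the plan says.** **Purpose.** The SAP, under Aims, sets out "to improve the early prediction of the studied outcome" and refers to STARD.

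**Outcome.** The Protocol summary defines it as "Need for open heart surgery or cardiac catheter intervention to treat predefined congenital heart disease lesions leading to pulmonary over-circulation". The CMR item in the list of assessments for cases shows how it is counted: "subjects reaching outcome (undergoing open heart surgery / cardiac catheter intervention) on hospital admission before treatment". In practice, then, the event is undergoing the procedure. No objective criteria for need and no adjudication are described.

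**Eligibility.** Cases must be "without treated congenital heart disease by open heart surgery or cardiac catheter intervention at enrolment". Nothing is said about children whose procedure has been agreed but not yet done.

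**Visits.** The smallest schedule for a case is "Minimum 2 (at enrolment and 6-12 months after outcome is reached" (Protocol, Number of assessments). Enrolment can therefore be the only scheduled visit before the procedure.

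**Predictors.** For echo the SAP says "selected echocardiographic measure (test individual measures) will be selected to predict outcome (need for open heart surgery or cardiac catheter intervention", and it repeats the pattern for groups of echo measures, CMR and biomarkers. Data analysis adds logistic regression, ROC/AUC and a risk score. It does not say which visit supplies the predictor values, and it gives no minimum lead time or prediction horizon.

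**Setting.** The heading of the case assessments reads "Type of assessments in local paediatric cardiology hospital / out-patient clinic settings". Neither document says whether study echo results are withheld from those who decide on intervention. Images are stored for analysis, and biomarker samples are stored until batch analysis.

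**The concern.** A prediction is useful only if it comes before the thing predicted. For a child whose procedure is already decided, a measurement at enrolment comes after the decision that produces the event. If such children are pooled with children whose course is still open, and their findings are more marked, the AUC overstates how well the test separates children while the question is still undecided. The same data feed the logistic models and the risk score. Blood biomarkers drawn at enrolment are exposed as much as echo.

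A secondary question concerns echo itself. The outcome is a clinical decision, and the study echo is done in the local cardiology setting. If that echo informs the decision, its AUC is partly a measure of agreement with current practice. Batch-analysed biomarkers are not directly exposed to this. However, the SAP names no analysis of whether they add anything to echo.

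**Working it through.** **Nothing to reproduce.** The documents give power 0.8 and alpha 0.05, but no sample size, event count, AUC or share of already-decided children. Every input below other than the design facts is an assumption.

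**1. Can an already-decided child become a predicted event?** Take the rules in order.
- The child is untreated, so the eligibility rule is met.
- Echo and blood are taken at enrolment, after the decision.
- The procedure follows, so the outcome is reached. The two-assessment minimum allows this with no other scheduled visit in between.
- No lead-time or predictor-visit rule removes the child from the models.

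The answer is yes, from the written rules alone.

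**2. How much could it matter?** The AUC is the probability that a randomly chosen event scores higher than a randomly chosen non-event. Let *f* be the share of events already decided at enrolment. With the same non-events for both kinds of event, and a fixed score,

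AUC(pooled) = (1 − f) × AUC(undecided) + f × AUC(decided).

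With AUC(undecided) assumed to be 0.70:

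| f | AUC(decided) | Calculation | Pooled AUC |
|---|---|---|---|
| 0% | any | 1.00 × 0.70 | 0.70 |
| 5% | 0.80 | 0.95 × 0.70 + 0.05 × 0.80 | 0.705 |
| 10% | 0.80 | 0.90 × 0.70 + 0.10 × 0.80 | 0.71 |
| 30% | 0.80 | 0.70 × 0.70 + 0.30 × 0.80 | 0.73 |
| 30% | 0.90 | 0.70 × 0.70 + 0.30 × 0.90 | 0.76 |
| 50% | 0.95 | 0.50 × 0.70 + 0.50 × 0.95 | 0.825 |

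The excess is f × [AUC(decided) − AUC(undecided)]. It is zero if no such child enrols or if the two AUCs are equal.

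**3. Secondary: echo and the decision.** In a simulation of 400,000 subjects, latent need and an echo score are correlated 0.3. Intervention goes to the top 20% on a weighted sum of the two, with weight *w* on echo. The echo AUC is 0.65 at w = 0, 0.77 at w = 0.25 and 0.90 at w = 0.50. With no correlation between echo and latent need, the values are 0.50, 0.66 and 0.85. The documents do not give *w*.

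**4. Secondary: biomarkers that only track echo.** In a simulation of 2 million subjects, the decision is the top 30% of echo plus noise.
- Noise SD 0.5: the echo AUC is 0.94. Markers correlated 0.3, 0.5 and 0.7 with echo, with no information of their own, have AUCs of 0.63, 0.71 and 0.80.
- Noise SD 2: the echo AUC is 0.71, and the same three markers range from 0.56 to 0.65.

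These are the markers' true AUCs for this outcome. What they show is that a marker's AUC on its own cannot reveal whether it adds to echo.

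**The case against.** The strongest reply is that all this rests on silence in short documents. The Protocol text is a summary. It does not say that already-decided children will be enrolled, how many there might be, or that clinicians use the study echo. Stored images and anonymised analysis are compatible with masked offline reading. The echo measures tested need not be those that drive decisions.

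Much of this stands. A reader might infer that AUCs *are* inflated. The documents do not support that: they only fail to prevent it, and at 5–10% decided with AUC 0.80 in those children the excess is 0.01 or less. A reader might also infer that a biomarker correlated with echo has an inflated AUC. It does not; whether it adds to echo is a different question. Such a marker could also be of use earlier than echo or in its place. Dried blood from neonatal screening will usually predate any decision, so the timing argument hardly reaches those samples.

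Leaving decided children out also has a price: it may remove the most severe cases and narrow the spectrum. That is a reason to report results both ways.

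The gap itself remains. An aim of early prediction needs a rule that predictors precede the decision, and neither document has one.

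**Conclusion.** The concern holds as a gap in the plan. Followed as written, the plan can score a measurement taken after the decision as a prediction. The eligibility rule, the event definition and the absence of a predictor visit and lead time are enough to establish this; no assumption about clinical practice is needed.

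The size cannot be fixed from the documents. Across the assumed inputs, a true AUC of 0.70 would be reported as anything from 0.70 to about 0.83. An upward direction requires that already-decided children are better separated from non-events than undecided ones, which is plausible but assumed. The mixture formula is for a fixed score; refitting a model on the pooled events could also change its coefficients.

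The link between echo and the decision, and the untested added value of biomarkers, are secondary. They bear on how the results are described, and they do not show that any particular AUC is wrong.

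**What to change.** In the SAP:

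1. **Decision status and timing.** Record at enrolment whether intervention has already been decided, with a working definition (for example, accepted or listed for a procedure), and record the decision date for every case. Take predictors from the enrolment visit and state in advance a minimum lead time from that visit to the decision. The lead time matters because a status item alone would still admit decisions made at or just after enrolment. Exclude already-decided children from the primary prediction models, ROC analysis and risk score, and report AUCs with them included as a sensitivity analysis. Keep them in the descriptive, CMR and pre/post analyses. This rule is for echo and biomarkers: CMR in cases is scheduled only at admission and after the procedure, so it needs separate thought.
2. **Added value.** As a secondary analysis, report each biomarker's gain in AUC and its likelihood-ratio test over a small base model (age, lesion, routine enrolment echo), sized to the number of events.
3. **Description.** State that echo-only AUCs may partly reflect agreement with current decisions.

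The cost is two case-form entries (status and date) and some SAP wording. Decision status is best captured at enrolment, since it may be hard to reconstruct later. The downside is fewer events in the primary models and possibly less favourable AUCs. Clinical management is unaffected.

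### The SAP plans to use CMR measures to predict need for intervention, but the only cases scanned are those that have already reached that outcome, so the prediction cannot be estimated

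*SAP*

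**What the plan says.** The SAP's Aims section sets out diagnostic test evaluations intended "to improve the early prediction of the studied outcome (need for open heart surgery or cardiac catheter intervention in cases". Diagnostic methods then gives echocardiography, CMR and biomarkers the same two-part aim, once for single measures and once for groups of measures. For CMR the single-measure line reads "selected CMR measure (test individual measures) will be selected to predict outcome (as above".

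Data analysis names the tools and the population. Logistic regression is to "create models that are suitable to predict outcome in cases (need for open heart surgery or cardiac catheter intervention". ROC/AUC is described as "analysis for proposed new diagnostic tests that may help to predict outcome in cases (see above". A risk score, also in cases, follows. None of these lines exempts CMR.

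The protocol sets out who is scanned. In the list of assessments for cases, item 4 provides CMR "for subjects reaching outcome (undergoing open heart surgery / cardiac catheter intervention) on hospital admission before treatment and 6-12 months after intervention in ambulatory setting". The summary table agrees, giving two CMR assessments for cases reaching the outcome. Its footnote defines the CMR population as "Subgroup of cases reaching outcome during study and subgroup of matched controls". Item 4 of the list for controls gives a matched subgroup one scan, for comparison with the cases that reach the outcome.

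**The concern.** A prediction model for need of intervention has to compare children with heart disease who went on to need it with children with heart disease who did not. The CMR schedule supplies only the first group. The SAP nevertheless treats CMR like echocardiography and blood biomarkers, which are collected from every case at enrolment.

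One of the three named diagnostic methods therefore cannot meet its stated aim, and the SAP does not warn the analyst. There is also a risk in how the gap might be filled. The only other children with CMR are healthy controls. If they were used as non-events the software would return an AUC, and that figure could be reported as accuracy for predicting intervention when it measures how well CMR separates treated heart disease from health.

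**Working it through.** The plan states no sample size, event count or target AUC for CMR, so there is no figure to reproduce. The check asks whether the quantity can be estimated at all.

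**Step 1: who has CMR, by outcome status** (protocol assessment lists, summary table and footnote)

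| Group | Followed in study | CMR | Can show the outcome? |
|---|---|---|---|
| Cases reaching the outcome | yes | on admission for intervention, and 6-12 months after | yes, all of them |
| Cases not reaching the outcome | yes, annually to at most 3 years | none scheduled | no, these are the non-events |
| Matched controls | enrolment only | one scan | not at risk: no cardiovascular disease by definition |

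**Step 2: estimability among cases.** Let n1 be the number of scanned cases with the outcome and n0 the number without it. By design n0 = 0.

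- AUC is the proportion of event/non-event pairs that are correctly ordered. The number of pairs is n1 × n0. For n1 = 20, 50 or 100 this is 20 × 0 = 50 × 0 = 100 × 0 = 0.
- Specificity has n0 = 0 as its denominator and is undefined.
- In logistic regression the response equals 1 for every scanned case, so there is no finite slope estimate and no odds ratio.

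No increase in n1 changes any of these results.

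**Step 3: timing.** The first scan takes place on admission for the intervention, when the need for it has already been decided. The second comes after treatment. No scan in cases is scheduled at enrolment or at an annual visit, so none is available at a point where prediction would be early.

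**Step 4: what happens if controls stand in as non-events.** This is an illustration with assumed values; the documents give no CMR means. Take a measure that is normal with SD 1 in every group and mean 0 in healthy controls, m0 in cases without the outcome and m1 in cases with it. Then

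- AUC against healthy controls = Φ(m1/√2)
- AUC among cases = Φ((m1 − m0)/√2)

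| m1 | m0 | AUC against healthy | AUC among cases |
|---|---|---|---|
| 2.0 | 0.5 | Φ(1.414) = 0.921 | Φ(1.061) = 0.856 |
| 2.0 | 1.0 | 0.921 | Φ(0.707) = 0.760 |
| 2.0 | 1.5 | 0.921 | Φ(0.354) = 0.638 |
| 2.0 | 2.0 | 0.921 | Φ(0) = 0.500 |
| 1.5 | 1.0 | Φ(1.061) = 0.856 | Φ(0.354) = 0.638 |

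The first formula does not contain m0. The comparison with healthy children therefore carries no information about how well CMR separates cases who need intervention from cases who do not. It overstates that separation whenever cases without the outcome lie between healthy children and cases with it. With m1 = 2.0 the overstatement runs from 0.921 − 0.856 = 0.065 to 0.921 − 0.500 = 0.421.

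**The case against.** The strongest reply is that the CMR data already have a planned analysis that can be carried out. The SAP's Data analysis section includes tests comparing controls with cases and tests of change in cases over follow-up, and the protocol says the control scans are there for comparison with outcome cases. On this view the fault is an aim carried over into two CMR lines, and the analyst is not forced to choose between a failed model and a misuse of controls. The inflated AUC is also hypothetical: the SAP confines prediction to cases, and nothing in either document proposes using healthy controls as non-events. Finally, the size of any inflation depends on assumed means and could be as small as about 0.07.

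Much of this is fair. The comparative and paired analyses are indeed available, and the AUC figures are illustrative only. But those analyses do not answer the prediction aim, which stays in the SAP as written. The finding that CMR prediction cannot be estimated rests on the schedule alone and needs none of the assumed values.

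The objection also notes that removing the aim is not the only remedy. That is correct: CMR could instead be obtained before the outcome is determined, in cases including those who never reach it. That would be a change to the protocol, and its feasibility is for the sponsor to judge.

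**Conclusion.** The concern holds. The two CMR prediction lines in the SAP conflict with the CMR schedule in the protocol. There are zero scanned cases without the outcome, so AUC, specificity and odds ratios for CMR within cases are not estimable at any sample size. The timing of the first scan separately rules out early prediction. This conclusion assumes only that scans follow the protocol's text, table and footnote, which agree with one another.

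The possible overstatement if controls were substituted is a secondary point. Its size rests on assumed means and equal SDs and should be read as a range.

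The problem is confined to CMR. Echocardiography and blood samples are scheduled in all cases from enrolment, so this objection does not touch the prediction aims for those two methods. The SAP should be corrected before analysis, because one of its three diagnostic aims cannot be carried out as written.

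**What to change.** In the SAP, remove CMR from the outcome-prediction aim and state that the logistic regression, ROC/AUC and risk-score analyses do not include CMR measures. Replace the two CMR lines with aims the schedule supports:

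- comparison of pre-intervention CMR measures in cases reaching the outcome with those in matched controls;
- paired change in CMR measures from before intervention to 6-12 months after it.

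Add a sentence saying that CMR contrasts between cases and healthy controls will not be reported as accuracy for predicting need for intervention.

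The cost is SAP wording only: no new scans, visits or data. What is given up is a CMR prediction claim that the design cannot support. If the sponsor wishes to keep that claim, the protocol would have to provide CMR before the outcome is determined in cases, including those who do not go on to reach it.
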